8.8.1 Prior and Concomitant Medication

Eligible subjects are healthy volunteers. It is expected that in the period before the start of the study they will have taken only infrequent medication to treat intercurrent conditions.

Subjects will be excluded if they have taken any prescription or nonprescription drug, vitamin, dietary supplement and/or herbal supplement that is a strong inducer of cytochrome P450 (CYP) metabolizing enzymes within 1 month, or any prescription or nonprescription drug, vitamin, dietary supplement and/or herbal supplement within 1 week (or 5 half-lives, if longer) before the first dose of study medication, with the exception of acetaminophen (paracetamol) at doses up to 2100 mg/day.

Subjects will also be excluded if they have taken any medication which will alter endogenous hormone levels especially hormonal contraceptives (given by any route) for the periods prior to the screening visit, as follows:

- ≥ 1 week for vaginal hormonal products (rings, creams, gels and including dehydroepiandrosterone [DHEA] or analogues thereof)
- ≥ 4 weeks for transdermal estrogen alone or estrogen/progestin products
- ≥ 8 weeks for oral estrogen (including selective estrogen receptor modulators) and/or progestin therapy
- ≥ 8 weeks for intrauterine progestin therapy
- ≥ 3 months (after removal or end of 5-year duration) for progestin implants and ≥ 3 months for estrogen alone injectable drug therapy
- ≥ 6 months for estrogen pellet therapy or progestin injectable drug therapy

Subjects must not discontinue prescribed medication to comply with these restrictions without prior approval from the prescriber.

Permitted concomitant medication comprises:

- Acetaminophen (paracetamol), at doses up to 2100 mg/day

- Medication needed to treat AEs. In selecting appropriate medication, the Investigator must consider the risk of drug-drug interaction involving NT-814 either as substrate or as perpetrator. See [Section 4.5.2](#) for further information or contact the Sponsor's Medical Monitor. If concomitant medication needed to treat AEs is likely to be associated with increased risk to the subject or reduce the likelihood of achieving the study objectives, the subject should discontinue dosing with study medication and/or be withdrawn from the study.

With these exceptions, no other concomitant medication is allowed during this study from 1 week before first administration of study medication until the follow-up visit.

If the administration of any concomitant therapy becomes necessary, it must be reported on the appropriate eCRF page. The sponsor must be notified in advance (or as soon as possible thereafter) of any instances in which prohibited therapies are administered.

8.8.2 Contraception

All subjects must agree to use two acceptable methods of birth control for the duration of participation in the study and 30 days after the last dose, one of which must be a barrier method with spermicide.

Acceptable methods of birth control are:

- Surgical sterilization of the subject's male partner (vasectomy with documented azoospermia), if he is the sole partner of that subject;
- A non-hormonal intrauterine device (IUD) with failure rate of less than 1% per year inserted by qualified physician at least one month before study drug administration and to remain in place for at least 30 days after the last dose of study drug;
- Barrier methods such as male condom or cap, diaphragm or sponge with spermicide

Women who lead either an abstinent or an exclusively homosexual lifestyle are not required to use two methods of contraception but are required to commit to this lifestyle for the duration of the study and 30 days after the last dose.

Hormonal contraceptives are not acceptable by any route (systemic, implants, depot, intrauterine).

Serum pregnancy tests will be done on women of child-bearing potential at screening and on Day 21 or 22 of Cycle 1, and a urine pregnancy test performed on Day 1 or 2 of Cycle 2 (prior to the first dose of study medication). All tests must be negative for the subject to continue in the study.

A final serum pregnancy test will be done at the final follow up visit.

9 STUDY ASSESSMENTS AND PROCEDURES

Please see [Table 9-1](#) for the complete schedule of assessments. [Section 9.6](#) summarizes the order of procedures when more than one activity is scheduled for the same time point and permissible time windows.

Table 9-1 Schedule of Events

Day	Screening	Cycle 1					Cycle 2					Follow-up
	-21 ^a	1	3/4	9/10	15/16	21/22	1/2	3/4	9/10	15/16	21/22	35-38
Clinic visit (out-patient)	X		X	X	X	X	X					X ^e
Informed consent	X ^b											
Menstrual flow starts		X					X ^l					
Record dates of start of menstruation		X										X
Medical History	X											
Physical examination	X											X
Vital signs ^c	X					X	X ^f	X ^h	X ^h	X ^h	X	X
Oral or aural body temperature	X						X ^f					X
12-lead ECG	X					X	X ^f	X ^h	X ^h	X ^h	X	X
Weight	X					X	X					X
Serology ^d	X											
Drugs of abuse screen	X					X	X ^f					
Hematology and Clinical Chemistry	X					X	X		X		X	X
Serum pregnancy test	X					X						X
Urine pregnancy test							X ^f					
Sample for PD hormone assessment			X	X	X	X		X ^{h,i}	X ^{h,i}	X ^{h,i}	X ⁱ	
Sample for PK								X ^{h,j}	X ^{h,j}	X ^{h,j}	X ^j	
Randomization						X						
NT-814/placebo once daily							X					X ^g
Adverse Event / con med reporting ^k	X											X

- a Screening to be scheduled within 21 days of the anticipated start of the next menstrual cycle. This period can be extended if the menstrual period starts later than anticipated.
- b Informed consent can be obtained prior to the screening visit. The screening period starts from the date of the screening procedures, not from the date of consent.
- c Vital signs: systolic and diastolic blood pressure, pulse
- d Hepatitis B surface antigen, hepatitis B core antibody, hepatitis C antibody, human immunodeficiency virus
- e Daily clinic visits in the morning, starting on Day 1 or 2 of Cycle 2 and ending on Day 21/22.
- f Performed prior to the first dose
- g Doses administered in the morning, in the clinic ~1-2 hours after breakfast; starting on Day 1 or 2 of Cycle 2; last dose will be day prior to clinic visit on Day 21/22. Doses to be administered at the same time each day (±1hr).
- h Prior to administration of dose on the days shown
- i PD sample days must be the same relative to Day 1 on both Cycles 1 and 2
- j PK samples taken on same day/time as PD samples in Cycle 2
- k AEs and concomitant medication to be reported from the start of screening
- l Requires visual verification

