5 STUDY OBJECTIVES AND CORRESPONDING ENDPOINTS

The study objectives and corresponding endpoints/study outcomes are presented in [Table 5-1](#).

Table 5-1 Objectives and Corresponding Endpoints/Study Outcomes

Objectives	Endpoints/Study Outcomes
Primary	
To determine the effects of NT-814 given at doses of 40 mg, 80 mg, 120 mg, and 160 mg once daily for approximately 21 days on GnRH pathway hormones in healthy female subjects	
 • Change from baseline in serum LH, FSH, estradiol and progesterone over a full menstrual cycle
Secondary	
To evaluate the safety of NT-814	
 • 12-lead ECGs: abnormalities; change from baseline in quantitative parameters (RR interval, PR interval, QRS duration, absolute QT interval and QTcF) • Change from baseline in clinical laboratory assessments (hematology, biochemistry) • Change from baseline in vital signs (BP, pulse rate, weight) • Nature and severity of TEAE; withdrawals due to TEAE
Exploratory	
To evaluate the pharmacokinetic-pharmacodynamic (PK-PD) relationship of NT-814	
 • NT-814 plasma concentration levels concurrent with serum LH, FSH, estradiol and progesterone during Cycle 2
To evaluate the effect of NT-814 on menstrual cycle length	
 • Change from baseline (Cycle 1) in the length of the menstrual cycle

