Safety will be monitored throughout the study with routine safety assessments (AE recording; vital signs; 12-lead ECG; clinical laboratory tests). A physical examination will be conducted at screen and follow-up. Additional safety assessments will be done at any time as considered appropriate by the Investigator. Additional safety assessments not specified in the protocol may be performed as required by Quotient Sciences Standard Operating Procedures, but these will not be entered into the eCRF. Any abnormal assessments observed during non-protocol required safety assessments will be recorded as AEs if appropriate and the corresponding abnormal assessment entered as an unscheduled assessment in the eCRF.

Subjects will have a final outpatient follow-up visit two weeks following the final dose of study medication. At this visit the subject will be asked when their next menstrual cycle started (the cycle after the completion of dosing).

An overview of the study is shown in [Figure 6-1](#).

Figure 6-1: Study Schematic

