9.2.3 Vital Signs

Vital signs will be measured at the time points indicated in Table 9-1 and will include systolic and diastolic BP, pulse, temperature and weight.

BP and pulse should be measured using a standardized process:

- After the subject has been at rest supine for at least 5 minutes
- Not within 15 minutes after venipuncture or cannulation

- Using an automated BP device, with an appropriately sized cuff, with the bladder centered over the brachial artery
- Using the same arm throughout the study

All measurements are to be recorded on the eCRF.

All vital signs must be reviewed by the Investigator or a medically-qualified designee, who will comment on all abnormal results and determine whether they are clinically significant. These assessments will be recorded in the eCRF. Clinically significant findings must also be reported as AEs in the eCRF.

9.2.4 12-lead Electrocardiograms

12-lead ECGs will be recorded at the time points indicated in the Study Schedule in [Table 9-1](#). A single recording will be obtained after the subject has been at rest supine for at least 5 minutes and not within 15 minutes after venipuncture. An electronic copy or original paper copy (not a photocopy) of each ECG will be saved for possible future manual evaluation.

Cardiac intervals will be measured automatically, confirmed by the Investigator or a medically-qualified designee, and recorded. ECG intervals outside the local reference ranges or ECG interpreted as other than normal sinus rhythm or sinus arrhythmia should be commented on for clinical significance. The overall ECG must be reviewed by the Investigator or a medically-qualified designee and assigned one of the following categories:

- Normal
- Abnormal, not clinically significant
- Abnormal, clinically significant

All abnormalities, whether clinically significant or not, must be recorded in the eCRF. An abnormal, clinically significant, finding that is present at baseline must be recorded in the medical history. An emergent clinically significant ECG finding should be recorded as an AE.

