9.6 Priority Order of Study Assessments; Permitted Windows

Note the following with regard to sequence of tests and acceptable time windows.

- Informed consent can be obtained before the actual screening visit, with the 21-day screening period starting from the date of the screening visit and not the date consent is obtained
- Predose procedures on Day 1 or 2 of Cycle 2 must be completed before the first dose
- Assessments on Cycle 2 Days 3 or 4, 9 or 10, and 15 or 16 should be performed prior to dosing
- As far as possible, each subject should be dosed at the same time of day during the dosing period in Cycle 2; however, a window of ± 1 hr is permitted
- The serum hormone sampling days relative to Day 1 of Cycle 2 will match the days samples were taken in Cycle 1 (relative to Day 1 of Cycle 1) within each subject (e.g. if the subject attended the clinic on Day 4 in Cycle 1, the hormone sample must be taken on Day 4 in Cycle 2; if they attended on Day 9 in Cycle 1 the hormone sample must be taken on Day 9 in Cycle 2, and so on).
- Collection of samples for hormone assessment should be performed at approximately the same time of day throughout Cycles 1 and 2; however, a window of ± 1 hr is permitted
- Measurement of vital signs and ECG recordings should be avoided within 15 minutes after venipuncture and, therefore, should normally be done before blood sampling.

The Investigator may repeat tests, conduct tests other than those specified, and schedule additional visits in the event of a technical failure and/or if extra observations or samples of blood or urine are needed to monitor subject safety. These will not be considered protocol deviations.

Any deviation outside these permitted windows must be noted in the subject's clinic chart and eCRF.

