11.3.1 Baseline assessment

Descriptive statistics will be performed on relevant screening and baseline data (i.e. data collected prior to the treatment administration) and on demographic characteristics for each treatment group.

In general, baseline for safety assessments will be the last value recorded before the first dose of IMP. Baseline for PD assessments will be the time-matched value from Cycle 1.

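### Weight change is a secondary safety endpoint, but Table 9-1 marks no weight between Cycle 2 Day 1/2 and Follow-up, and footnote c conflicts with Section 9.2.3

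*Protocol*

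**What the plan says.** **Endpoint.** Table 5-1 (Section 5) and the synopsis list, under the secondary safety objective, "Change from baseline in vital signs (BP, pulse rate, weight"), with no time point named.

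**Schedule.** Section 9 refers the reader to Table 9-1 "for the complete schedule of assessments". Weight has a separate row there, with marks at Screening, Cycle 1 Day 21/22, Cycle 2 Day 1/2 and Follow-up. The vital signs row is marked at those visits and also at Cycle 2 Days 3/4, 9/10, 15/16 and 21/22, but footnote c defines it as "Vital signs: systolic and diastolic blood pressure, pulse".

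**Text definition.** Section 9.2.3 says that vital signs, at the Table 9-1 time points, "will include systolic and diastolic BP, pulse, temperature and weight". The safety assessments entry of the synopsis also puts weight among the vital signs.

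**Baseline and timing.** Section 11.3.1 says that in general "baseline for safety assessments will be the last value recorded before the first dose of IMP". Footnote g of Table 9-1 says that the "last dose will be day prior to clinic visit on Day 21/22". Section 6 says: "Subjects will have a final outpatient follow-up visit two weeks following the final dose of study medication".

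**The concern.** A change from baseline needs a post-baseline value at a time that bears on the treatment. As the table stands, the only such weight comes at Follow-up, after about two weeks without drug. A change that built up over 21 days of dosing and then reversed would leave no trace in the data. The analysis plan cannot repair this, because it cannot supply weights that were never recorded.

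The protocol gives some reason to want the end-of-dosing value. Section 4.2.2 attributes adverse findings in the 4-week animal studies to loss of appetite and dehydration, and Section 4.5.1 lists mild diarrhea among the expected reactions.

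The two definitions of vital signs add a practical risk: some staff may weigh subjects at every vital signs visit and others only where the weight row is marked.

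**Working it through.** **1. Position of the weight marks.** Table 9-1 has 12 visit columns, from Screening (1) to Follow-up on Day 35-38 (12).

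| Row | Columns marked | Marks strictly between Cycle 2 Day 1/2 and Follow-up |
|---|---|---|
| Weight | 1, 6, 7, 12 | 0 |
| Vital signs (footnote c: BP, pulse) | 1, 6, 7, 8, 9, 10, 11, 12 | 4 |
| Hematology and chemistry | 1, 6, 7, 9, 11, 12 | 2 (Days 9/10 and 21/22) |

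**2. Are the columns read correctly?** The table was extracted from PDF, so I compared rows with the text. Section 8.8.2 places serum pregnancy tests at screening, Cycle 1 Day 21 or 22 and the final follow-up, and the urine test at Cycle 2 Day 1 or 2. In the table these fall in columns 1, 6 and 12, and in column 7. Together they are exactly the columns of the weight row. Section 9.2.2 places the physical examination at screening and follow-up, which matches columns 1 and 12.

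**3. Which weight is the baseline?** Under Section 11.3.1 it is the last pre-dose value. The Cycle 2 Day 1/2 weight mark lacks the pre-dose footnote f, but Section 6 puts baseline safety assessments before randomization, and Section 9.6 says: "Predose procedures on Day 1 or 2 of Cycle 2 must be completed before the first dose". I therefore take the Cycle 2 Day 1/2 weight as baseline. One post-baseline mark remains, at Follow-up.

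**4. Time off drug at Follow-up.** The last dose is the day before the Day 21 or 22 visit, so Day 20 or Day 21. Days off drug = follow-up day − last-dose day:

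- 35 − 21 = 14
- 35 − 20 = 15
- 38 − 21 = 17
- 38 − 20 = 18

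The range is 14 to 18 days, in line with the two weeks stated in Section 6.

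**5. The two definitions side by side.** If the Section 9.2.3 list is applied to the vital signs row, weight is due at all four later Cycle 2 visits. If footnote c and the separate weight row are applied, it is due at none of them. The table reading is the more natural one: Section 9.2.3 takes its time points from the table, and temperature, which it also lists, likewise has its own row with fewer marks. The text does not say which definition governs.

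**The case against.** **No on-treatment weights at all?** A reader might infer that no subject in the trial will be weighed between the first dose and Follow-up. The documents do not establish that. It holds only if the table and footnote c override Section 9.2.3 and the synopsis. What can be said is what happens at a site that follows the table.

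**Extraction.** Some rows of Table 9-1 look displaced. The last clinic-visit and dosing marks sit under Follow-up although footnotes e and g end both around Day 21/22, and randomization sits under Cycle 1 although Section 8.3 puts it in Cycle 2. This is a fair reason to check the weight row against the source PDF. The agreement with Sections 8.8.2 and 9.2.2 makes misreading unlikely.

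**The endpoint can be computed.** Table 5-1 names no time point, and the schedule gives a baseline and one later value. That is true, but the later value describes the off-treatment state. The clinical safety sections name no weight effect of NT-814, which limits the stakes without removing the gap.

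**Menstrual-cycle confounding.** A reader might infer that cycle-related weight change would be mistaken for a drug effect. The randomized placebo group follows the same schedule, so ordinary cycle variation affects every arm. Only a treatment-induced change in cycle length could separate the arms. Section 4.1 reports an extended cycle with another NK3 antagonist, but the protocol says nothing about weight and cycle phase. A Cycle 2 Day 21/22 weight would share that limitation.

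**Half-lives.** Expressing the gap in half-lives adds little. The 20-22 hour figure in Section 4.3.1 comes from a hard-gel capsule in post-menopausal women, and nothing in the protocol ties weight recovery to plasma half-life. The days stand on their own.

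**Conclusion.** The point holds in a limited form. Footnote c and the weight row of Table 9-1 conflict with Section 9.2.3 and the synopsis. Under the table, there are 0 weight marks at the four Cycle 2 visits after Day 1/2, and the single post-baseline weight falls 14 to 18 days after the last dose. On that schedule the endpoint cannot show a weight change present at the end of dosing.

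This assumes that the weight row was extracted correctly, that sites work from the table, and that the Cycle 2 Day 1/2 weight is taken before the first dose.

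A reader might go further and infer that the baseline itself is wrong and should become Cycle 1 Day 21/22. The protocol does not support that: Section 11.3.1 uses the last pre-dose value for safety and keeps time-matched Cycle 1 values for the hormones.

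The consequence is modest, since weight is one of three items in a descriptive secondary safety endpoint of an exploratory Phase 1 study. The correction is worth making because it is specific and nearly free.

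**What to change.** 1. Add a weight mark at Cycle 2 Day 21/22 in Table 9-1.
2. Reconcile footnote c with Section 9.2.3 and the synopsis, so that one definition of vital signs applies and the weighing visits are unambiguous.
3. Keep the Section 11.3.1 baseline (last pre-dose value, normally Cycle 2 Day 1/2). Summarize change to Cycle 2 Day 21/22 by dose alongside placebo, and label the Follow-up weight as off-treatment.
4. Optionally, report Cycle 2 Day 21/22 minus Cycle 1 Day 21/22 as a supplementary summary. The Cycle 1 weight is already collected, and this needs no change to the baseline rule.

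The cost is one scale reading per subject (32 readings in Cohort 1, 42 with Cohort 2, before any replacements) at a visit already attended, plus one table mark and a short wording correction.

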9.1 Informed Consent and Screening

Subjects will be provided with the Participant Information Sheet and Informed Consent Form for their prior review. Written informed consent to participate in the study must be obtained for all subjects before any study-related procedures are performed; subjects must personally sign and date the approved ICF and, where applicable, privacy statement.

All subjects will be screened within 21 days of the expected start of Cycle 1. This period can be extended if the menstrual cycle starts later than anticipated.

9.2 Safety Assessments

9.2.1 Medical History and Concomitant Disease

History should include (but not be limited to) respiratory, cardiovascular, renal, gastrointestinal, hepatic, endocrine, hematological, neurological, psychiatric and any other diseases, and all current and past medications taken during the 3 months before the Screening Visit. In addition, the Investigator will record in the eCRF information to document compliance with Inclusion Criterion 7 (use of acceptable contraception) as applicable.

The Investigator must record all clinically relevant information, regardless of the time since the date of diagnosis.

9.2.2 Physical Examination

A full physical examination will be conducted at the screening and follow-up/early termination visits (Table 9-1) by the Investigator or a medically-qualified designee. A full physical examination comprises review of the following body systems:

- General appearance
- Skin
- Head, eyes, ears, nose and throat
- Respiratory
- Cardiovascular
- Abdomen (including liver and kidneys)
- Musculoskeletal
- Neurological

Formal physical examination is not required at other times, but a directed physical examination should be undertaken if indicated by an emergent AE.

Any abnormalities identified at the screening visit should be documented on the medical history eCRF page. Any new clinically significant changes identified at later time-points should be documented as an AE.

If an improvement/resolution of a physical examination finding documented in the subject's medical history/screening visit occurs during the study, it should be recorded in the source document. If there is resolution of a physical examination finding previously noted as an AE, then the event resolution and stop date should be recorded on the AE eCRF page and documented in the subject's notes.

9.2.3 Vital Signs

Vital signs will be measured at the time points indicated in Table 9-1 and will include systolic and diastolic BP, pulse, temperature and weight.

BP and pulse should be measured using a standardized process:

- After the subject has been at rest supine for at least 5 minutes
- Not within 15 minutes after venipuncture or cannulation

- Using an automated BP device, with an appropriately sized cuff, with the bladder centered over the brachial artery
- Using the same arm throughout the study

All measurements are to be recorded on the eCRF.

All vital signs must be reviewed by the Investigator or a medically-qualified designee, who will comment on all abnormal results and determine whether they are clinically significant. These assessments will be recorded in the eCRF. Clinically significant findings must also be reported as AEs in the eCRF.

9.2.4 12-lead Electrocardiograms

12-lead ECGs will be recorded at the time points indicated in the Study Schedule in [Table 9-1](#). A single recording will be obtained after the subject has been at rest supine for at least 5 minutes and not within 15 minutes after venipuncture. An electronic copy or original paper copy (not a photocopy) of each ECG will be saved for possible future manual evaluation.

Cardiac intervals will be measured automatically, confirmed by the Investigator or a medically-qualified designee, and recorded. ECG intervals outside the local reference ranges or ECG interpreted as other than normal sinus rhythm or sinus arrhythmia should be commented on for clinical significance. The overall ECG must be reviewed by the Investigator or a medically-qualified designee and assigned one of the following categories:

- Normal
- Abnormal, not clinically significant
- Abnormal, clinically significant

All abnormalities, whether clinically significant or not, must be recorded in the eCRF. An abnormal, clinically significant, finding that is present at baseline must be recorded in the medical history. An emergent clinically significant ECG finding should be recorded as an AE.

